13. Neurological findings consistent with Progressive Multifocal Leukoencephalopathy (PML) - not otherwise explained - or confirmed PML.
14. Electrocardiogram (ECG) showing a clinically significant abnormality at Screening or showing an average QTcB or QTcF interval ≥ 450 msec (≥ 480 msec for subjects with a Bundle Branch Block) over 3 consecutive ECGs (refer to Section 7.4.5)
15. ALT $>2\times$ ULN and bilirubin $>1.5\times$ ULN (isolated bilirubin $>1.5\times$ ULN is acceptable if bilirubin is fractionated and direct bilirubin $<35\%$).
16. Current or chronic history of liver disease, or known hepatic or biliary abnormalities (with the exception of Gilbert's syndrome or asymptomatic gallstones)

CONCOMITANT MEDICATIONS

17. Use of systemic immunosuppressive or immunomodulatory agents including methotrexate, azathioprine, leflunomide, mycophenolate (including mycophenolate mofetil, mycophenolate mofetil hydrochloride, and mycophenolate sodium), mizoribine, calcineurin inhibitors (e.g., tacrolimus, cyclosporine), sirolimus, 6-mercaptopurine, or thalidomide) within 60 days prior to Day 0.
18. Have received cyclophosphamide within 180 days prior to Day 0.
19. Have received anti-BLyS, anti-CD 20, anti-CD22 or anti-CD52 or any other B-cell depleting agent within 364 days prior to Day 0.
20. Have received abatacept or any biologic agent within 180 day prior to Day 0
21. Have received IVIG or plasmapheresis within 90 days prior to Day 0.
22. Have received oral steroid >10 mg prednisone equivalent/day within 30 days prior to

Day 0 or oral steroid >20 mg prednisone equivalent / day for a minimum of two consecutive weeks within 60 days prior to Day 0. Have received parenteral steroid within 60 days prior to Day 0.

23. Have received a live vaccine within 30 days of Day 0.
24. Current participation in any other interventional trial.
25. Planned blood donation during the treatment and follow up periods of the study.

RELEVANT HABITS

26. Subjects who are unable or unwilling to administer, or to have a caregiver administer subcutaneous injections.
27. Drug or alcohol abuse or dependence.

CONTRAINdications

28. History of hypersensitivity to belimumab and/or rituximab or known to have titers of human anti-mouse antibody or human anti-chimeric antibody or history of hypersensitivity reactions when treated with other diagnostic or therapeutic monoclonal antibodies.

DIAGNOSTIC ASSESSMENTS AND OTHER CRITERIA

29. Have an IgA deficiency (IgA level <10 mg/dL).

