6.9. Concomitant Medications and Non-Drug Therapies

6.9.1. Permitted Medications and Non-Drug Therapies

- Oral steroids (provided subject is on a stable regimen for at least 30 days at a dose no greater than 10 mg prednisone equivalent daily prior to Day 0 and continues this dose for the duration of the study).
- Hydroxychloroquine (provided subject is on a stable regimen no greater than 400 mg po qd (ie daily) for 30 days prior to Day 0 and continues this dose for the duration of the study).
- Topical symptomatic therapies are detailed below:
 - Ophthalmic lubricants [(e.g. glucane or saline eye drops); subjects will be required to withhold dosing 4hrs prior to efficacy assessments].
 - Ophthalmic lubricating ointments [(e.g. Dry Eyes, LacriLube); subjects will be required to withhold dosing 24hrs prior to efficacy assessments].
 - Hydroxyl cellulose ophthalmic insert [(e.g. Lacrisert); subjects will be required to withhold dosing 24hrs prior to efficacy assessments].

- Non-pharmacologic saliva stimulants [(e.g. gums, drinks, teeth washing); subjects will be required to withhold dosing 90 minutes prior to efficacy assessments].
- Saliva substitutes [(e.g. Xialine, Oral Balance , Saliva Orthana , Salinum mouth rinses, Chlorhexidine mouth rinses); subjects will be required to withhold dosing 90 minutes prior to efficacy assessments].
- Oral muscarinic agonists (such as pilocarpine and cevimeline) provided subjects are on a stable regimen for at least 30 days prior to Day 0 and continue this dose for the duration of the study. Subjects will be required to withhold dosing with these agents in the 24h prior to all efficacy assessments.
- Anticholinergic agents, such as tricyclic antidepressants, bupropion, antihistamines, phenothiazines, antiparkinsonian drugs, anti-asthmatic medications, or gastrointestinal (GI) medications that cause xerostomia in more than 10% of patients, provided that a subject is on a stable regimen for at least 30 days prior to Day 0.

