6.9.2. Prohibited Medications and Non-Drug Therapies

- Concomitant biologic treatments (see SRM for examples)
- Conventional systemic immunosuppressive treatments and DMARDs (such as methotrexate and azathioprine) (see SRM for examples)
- Pharmacological topical ophthalmic agents (e.g. NSAIDs, corticosteroids, cyclosporine, diquafosol) are excluded from use in the study.
- Non muscarinic secretagogues (e.g. Anetholtritione, Bromhexine3 N-acetylcysteine) are excluded from use in the study.

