7.1. Time and Events Table

Study Day	Screening (up to 35 days prior to Day 0)	Day 0	7 ± 1 days	28 ± 7 days	56 ± 7 days	70 ± 7 days	84 ± 7 days	112 ± 7 days	140 ± 7 days	168 ± 7 days	196 ± 7 days	224 ± 7 days	252 ± 7 days	280 ± 7 days	308 ± 7 days	336 ± 7 days	364 ± 7 days	General follow up period ¹	Individualized follow up period (IFU) ⁶	IFU Final Visit	
Study Week	W -5		W1	W4	W8	W10	W12	W16	W20	W24	W28	W32	W36	W40	W44	W48	W52	W68			
Informed consent	X																				
Inclusion and exclusion criteria	X																				
Demography	X																				
Full physical exam	X	X ³																	X	X	X
Abbreviated physical exam symptom directed			X	X	X	X	X	X	X	X	X	X	X	X	X	X	X		X		
Past & current medical conditions [including AECG criteria & CV medical history]	X																				
Urine pregnancy test (WCBP) in clinic ⁹	X	X ³		X	X		X	X	X	X	X	X	X	X	X	X	X	X	X	X	
Concomitant medication review	X ¹⁰	X ³	X	X	X	X	X ¹⁰	X	X	X ¹⁰	X	X	X ¹⁰	X	X	X	X ¹⁰	X ¹⁰	X	X ¹⁰	
Randomization		X																			
Belimumab/placebo, (weekly, home, except 1 st & 2 nd dose), last dose wk 51		X ¹¹	X ¹¹	X	X	X	X	X	X	X	X	X	X	X	X	X	X	X			
Monitor in clinic after dosing for 3hrs (1 st & 2nd dose of belimumab/pbo)		X	X																		
Rituximab/placebo (at site)						X ⁸	X ⁸														
Monitor in clinic after dosing for 1h post rituximab/placebo						X	X														

Study Day	Screening (up to 35 days prior to Day 0)	Day 0															General follow up period ¹	Individualized follow up period (IFU) ⁶	IFU Final Visit
		W -5	W1	W4	W8	W10	W12	W16	W20	W24	W28	W32	W36	W40	W44	W48	W52	W68	
ESSDAI ¹⁶	X						X			X			X				X	X	X
ESSPRI	X						X			X			X				X	X	X
Oral Dryness numerical resp. scale	X						X			X			X				X	X	X
Ocular Dryness numerical resp. scale	X						X			X			X				X	X	X
Salivary gland biopsy	X ⁵								X ¹²								X ¹³		
Lacrimal function (Schirmer's) test	X						X			X			X				X		
Fatigue- (PROFAD SSI SF)	X								X			X					X		
Patient Global Assessment (PtGA)	X								X			X					X		
Physicians Global Assessment (PGA)	X								X			X					X		
Exit interview ¹⁹																	X		
Stimulated Salivary Flow	X						X			X			X				X	X	X
Unstimulated Salivary Flow	X						X			X			X				X	X	X
Blood: Leukocyte population ²	X	X ³	X	X	X		X		X	X		X		X		X	X	X	X
Serological biomarkers	X	X ³			X		X	X	X	X		X		X		X	X	X	X
Saliva sample for proteomics	X						X		X			X				X			
Blood: BLyS levels ²		X ³		X	X		X	X	X	X		X		X		X	X	X	X
Blood: Transcriptomics		X ³			X				X			X				X			

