7.2. Screening and Critical Baseline Assessments

Information collected during the Screening Phase assessments described below represents key data that identifies and defines subject baseline status. This information is critical for the evaluation and comparison of subsequent safety and efficacy assessments.

Informed Consent: Informed consent will be obtained from the subject prior to the initiation of any study procedures or study-specific data collection.

Subjects who give written informed consent will enter a screening period of up to 35 days. A subject may be randomized when all screening procedures have been completed and eligibility criteria confirmed. During the screening period the following assessments will be performed:

Demographic parameters will be captured: year of birth, sex, race and ethnicity.

Medical/medication/family history will be assessed as related to the inclusion/exclusion criteria listed in Section 5. A complete medical history will be taken at the screening visit. Information from the medical history is important to establish the baseline condition of the subject, and will impact the safety monitoring assessments during the study. Any significant medical conditions affecting the subject in the past 5 years should be recorded on the Medical Conditions page of the eCRF. The history should include the following:

- Past or current conditions.
- Prior surgical procedures.
- Pharmacotherapy and chronic or recent use of any medication or herbal preparation.
- Prior immunosuppressive therapies, including type, number, and duration.
- Allergies and significant allergic reactions.
- Significant infections, or history of recurrent infection, including urinary and respiratory tract infections.
- Smoking history (current or previous smoker, number of cigarettes smoked per day).
- Cardiovascular medical history/risk factors (as detailed in the eCRF).

Urine Pregnancy Test: A test will be performed for women of child-bearing potential: monthly during the double blind treatment with investigational product (up to Week 52) and then at each clinic visit during the general and individualized follow up phases (see Time and Events Table in Section 7.1). Refer to the pregnancy section (Section 7.4.2).

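### The 30-day background-drug stability rules count back from Day 0, but the only pre-treatment ESSDAI, salivary flow and dryness values are taken at Screening, up to 35 days earlier, so baseline can precede or barely follow a regimen change.

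*Protocol*

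**What the plan says.** **When baseline is measured.** The Time and Events Table (Protocol 7.1) marks ESSDAI, oral and ocular dryness, and stimulated and unstimulated flow in the column headed "Screening (up to 35 days prior to Day 0", and next at Week 12. None is marked on Day 0. Section 7.2 states that "Subjects who give written informed consent will enter a screening period of up to 35 days" and that the information gathered there "represents key data that identifies and defines subject baseline status". Several laboratory measures, such as leukocytes, BLyS and immunoglobulins, do have a pre-dose Day 0 sample.

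**When background therapy must be stable.** Section 6.9.1 counts from Day 0 throughout:
- Oral steroid needs a "stable regimen for at least 30 days at a dose no greater than 10 mg prednisone equivalent daily prior to Day 0", with that dose then held.
- Hydroxychloroquine has the same 30-day window and is then held.
- Muscarinic agonists are allowed "provided subjects are on a stable regimen for at least 30 days prior to Day 0 and continue this dose", and are also withheld for 24 hours before every efficacy assessment.
- Anticholinergic agents need 30 stable days before Day 0. No withholding rule is given, and nothing says that the dose must be held afterwards.

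**Exclusions.** Criterion 22 in section 5.2 excludes oral steroid above 10 mg prednisone equivalent per day in the 30 days before Day 0. The other drug washouts run 60 days or longer, for example "Have received parenteral steroid within 60 days prior to Day 0".

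**Barred agents.** Section 6.9.2 states: "Non muscarinic secretagogues (e.g. Anetholtritione, Bromhexine3 N-acetylcysteine) are excluded from use in the study". It treats pharmacological topical eye agents the same way. Section 5.2 sets no entry interval for either.

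**The concern.** A stability rule is there so that baseline and later values are measured under the same background treatment. Here the rule protects Day 0, when no efficacy value is taken, and leaves part of the period in which baseline is taken unprotected. A change of steroid, hydroxychloroquine or anticholinergic between the screening assessment and Day 0 then counts as change from baseline, as if it had followed randomisation.

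The affected quantities matter. Section 9.4.3 analyses change from baseline in ESSDAI, stimulated flow and oral dryness. Section 9.2.1 mentions 30% responder endpoints for oral dryness and flow, which depend directly on each subject's own baseline. Screening ESSDAI also decides eligibility (at least 5 points) and the randomisation stratum (5-12 or above 12). The placebo arm starts at about 10 subjects, so a few odd baselines can move its mean by chance.

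**Working it through.** **Inputs.** Screening lasts up to 35 days (7.1, 7.2). The stability windows and the oral steroid limit are 30 days (6.9.1, criterion 22). Other washouts are 60, 90, 180 and 364 days (criteria 17 to 22). The SD of ESSDAI change is 4.192, with arms of 10 and 20 initially and 25 and 45 after the largest expansion (9.2.1).

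**The plan's own figures.** With SD 4.192 and a difference of 3, the normal approximation for 25 placebo subjects against 45, 40, 35 and 30 active gives power of 81.8%, 80.2%, 78.0% and 75.3%. The plan states 82%, 80%, 78% and 75%, so the table reproduces. For 10 against 20, the standard error is 4.192 × √(1/10 + 1/20) = 1.62. The smallest significant difference is 3.33 by the t distribution and 3.18 by the normal; the plan states 3.30. The date arithmetic below does not depend on these figures, which serve only for scale.

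**Date arithmetic.** For a window of w days and a baseline on Day -35, the guaranteed time stable or off drug at baseline is w - 35.

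| Rule | w | w - 35 | Days of screening not covered |
|---|---|---|---|
| Stability rules; oral steroid above 10 mg | 30 | -5 | 5 (Day -35 to Day -31) |
| Immunosuppressants; parenteral steroid | 60 | 25 | 0 |
| IVIG or plasmapheresis | 90 | 55 | 0 |
| Cyclophosphamide; other biologics | 180 | 145 | 0 |
| B-cell-directed agents | 364 | 329 | 0 |

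Only the 30-day rules leave a gap. For a baseline d days before Day 0, guaranteed stability is max(0, 30 - d): 0 days at d = 30 or more, 10 at d = 20, 20 at d = 10.

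**A compliant case.** A subject is rated for ESSDAI on Day -35 while taking 20 mg prednisone and takes a stable 10 mg from Day -31. The 30-day limit is met. The second oral steroid limb of criterion 22 concerns doses above 20 mg, so it is not triggered. Section 6.9.1 is met. Baseline was nevertheless rated at twice the dose that section 6.9.1 then holds for the rest of the study.

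**Scale, on assumptions the document does not supply.**
- If assessment days were spread evenly over Day -35 to Day 0, 5/36 = 14% of subjects, about 10 of 70, would be assessed in the uncovered days. Only those whose regimen then changed would be affected.
- If a fraction f had a baseline shift of s points, independent of other variation and with no baseline adjustment, the SD of change becomes √(4.192² + f(1 - f)s²). For f = 5% and s = 1 this is 4.20; for f = 14% and s = 5 it is 4.54. Power at 25 against 45 falls from 81.8% to 81.7% and 75.5% respectively.
- If k of 10 placebo subjects shifted by 3 to 5 points and no active subject did, the placebo mean would move by k × (3 to 5)/10: 0.3 to 0.5 for k = 1 and 0.6 to 1.0 for k = 2. Against a standard error of 1.62 that is about 0.2 to 0.6 standard errors.

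**The case against.** Several points on the other side stand.

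- **Longer washouts.** A reader might infer that the 60-, 90- and 180-day washouts are also undermined. They are not. Each exceeds 35 days, so the subject is already off drug at baseline, only for a shorter time than at Day 0.
- **Muscarinic agonists.** Someone who starts one after the screening assessment looks like a clear example but is a weak one, because dosing is withheld for 24 hours before each efficacy assessment. Steroids and anticholinergics have no such safeguard.
- **Secretagogues and eye agents.** A reader might infer that these may be used up to baseline and stopped later. Section 6.9.2 bars them in the study, and that can be read as starting at consent, before any assessment. What stands is that the start of the bar is unstated.
- **Bias.** A reader might infer a biased treatment comparison. Randomisation, stratified by baseline ESSDAI, exposes every arm equally in expectation, and drug starts and tapers can pull in opposite directions.
- **Repeat assessments.** Section 5.3 lets the investigator repeat screening assessments, so a subject can be re-rated after a change. This is discretionary and does not close the gap.
- **Stakes.** Safety is primary, the efficacy comparisons are exploratory, and the study is not powered for a set difference. That limits the weight of the point, but small exploratory arms have little tolerance for avoidable noise.

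**Conclusion.** The point holds for the 30-day rules only. A compliant subject can have the efficacy baseline taken on Day -35 to Day -31 under a regimen that is then changed, or later in screening with fewer than the 30 stable days that the protocol itself asks for before Day 0. The consequences are extra noise in change from baseline and responder status, possible misplacement at the ESSDAI entry threshold and stratum boundary, and chance imbalance in a placebo arm of about 10. There is no bias in the between-arm contrast in expectation.

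The 5-day gap and the max(0, 30 - d) rule follow from the protocol's own dates. The size of the effect does not. The share of subjects affected and the shift per subject are not in the document, and under the assumed ranges the result runs from a negligible loss of power to about 6 points (81.8% to 75.5%) at 25 against 45. This is a worthwhile correction to the wording, not a flaw that undermines the trial.

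**What to change.** Reconcile section 6.9.1 and the 30-day oral steroid limit in criterion 22 with sections 7.1 and 7.2, so that the baseline efficacy assessments are taken once the subject is already on the stable regimen carried into the study. The direct way is to tie the existing 30-day requirement to the date of those assessments. Guaranteed stability at baseline then rises from as little as 0 days to 30, and the uncovered gap falls from 5 days to 0. State also that the section 6.9.2 bar on secretagogues and pharmacological eye agents applies before those assessments.

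Leave the washouts of 60 days or more as they are. Counting them from screening would lengthen the time off treatment by up to 35 days with no need shown. No dose or washout length is proposed here.

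The cost is wording, plus a later baseline assessment or later screening for some candidates with a recent regimen change. Planned numbers and power are unchanged, and no visit is added.

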6.9.2. Prohibited Medications and Non-Drug Therapies

- Concomitant biologic treatments (see SRM for examples)
- Conventional systemic immunosuppressive treatments and DMARDs (such as methotrexate and azathioprine) (see SRM for examples)
- Pharmacological topical ophthalmic agents (e.g. NSAIDs, corticosteroids, cyclosporine, diquafosol) are excluded from use in the study.
- Non muscarinic secretagogues (e.g. Anetholtritione, Bromhexine3 N-acetylcysteine) are excluded from use in the study.

7. STUDY ASSESSMENTS AND PROCEDURES

Protocol waivers or exemptions are not allowed with the exception of immediate safety concerns. Therefore, adherence to the study design requirements, including those specified in the Time and Events Table, are essential and required for study conduct.

This section lists the procedures and parameters of each planned study assessment. The exact timing of each assessment is listed in the Time and Events Table, Section [7.1](#).

7.1. Time and Events Table

Study Day	Screening (up to 35 days prior to Day 0)	Day 0	7 ± 1 days	28 ± 7 days	56 ± 7 days	70 ± 7 days	84 ± 7 days	112 ± 7 days	140 ± 7 days	168 ± 7 days	196 ± 7 days	224 ± 7 days	252 ± 7 days	280 ± 7 days	308 ± 7 days	336 ± 7 days	364 ± 7 days	General follow up period ¹	Individualized follow up period (IFU) ⁶	IFU Final Visit	
Study Week	W -5		W1	W4	W8	W10	W12	W16	W20	W24	W28	W32	W36	W40	W44	W48	W52	W68			
Informed consent	X																				
Inclusion and exclusion criteria	X																				
Demography	X																				
Full physical exam	X	X ³																	X	X	X
Abbreviated physical exam symptom directed			X	X	X	X	X	X	X	X	X	X	X	X	X	X	X		X		
Past & current medical conditions [including AECG criteria & CV medical history]	X																				
Urine pregnancy test (WCBP) in clinic ⁹	X	X ³		X	X		X	X	X	X	X	X	X	X	X	X	X	X	X	X	
Concomitant medication review	X ¹⁰	X ³	X	X	X	X	X ¹⁰	X	X	X ¹⁰	X	X	X ¹⁰	X	X	X	X ¹⁰	X ¹⁰	X	X ¹⁰	
Randomization		X																			
Belimumab/placebo, (weekly, home, except 1 st & 2 nd dose), last dose wk 51		X ¹¹	X ¹¹	X	X	X	X	X	X	X	X	X	X	X	X	X	X	X			
Monitor in clinic after dosing for 3hrs (1 st & 2nd dose of belimumab/pbo)		X	X																		
Rituximab/placebo (at site)						X ⁸	X ⁸														
Monitor in clinic after dosing for 1h post rituximab/placebo						X	X														

Study Day	Screening (up to 35 days prior to Day 0)	Day 0															General follow up period ¹	Individualized follow up period (IFU) ⁶	IFU Final Visit
		W -5	W1	W4	W8	W10	W12	W16	W20	W24	W28	W32	W36	W40	W44	W48	W52	W68	
ESSDAI ¹⁶	X						X			X			X				X	X	X
ESSPRI	X						X			X			X				X	X	X
Oral Dryness numerical resp. scale	X						X			X			X				X	X	X
Ocular Dryness numerical resp. scale	X						X			X			X				X	X	X
Salivary gland biopsy	X ⁵								X ¹²								X ¹³		
Lacrimal function (Schirmer's) test	X						X			X			X				X		
Fatigue- (PROFAD SSI SF)	X								X			X					X		
Patient Global Assessment (PtGA)	X								X			X					X		
Physicians Global Assessment (PGA)	X								X			X					X		
Exit interview ¹⁹																	X		
Stimulated Salivary Flow	X						X			X			X				X	X	X
Unstimulated Salivary Flow	X						X			X			X				X	X	X
Blood: Leukocyte population ²	X	X ³	X	X	X		X		X	X		X		X		X	X	X	X
Serological biomarkers	X	X ³			X		X	X	X	X		X		X		X	X	X	X
Saliva sample for proteomics	X						X		X			X				X			
Blood: BLyS levels ²		X ³		X	X		X	X	X	X		X		X		X	X	X	X
Blood: Transcriptomics		X ³			X				X			X				X			
Salivary gland: Transcriptomics	X								X								X ¹³		
Blood: PBMC exploratory endpoints		X ³			X				X										
Blood: Belimumab PK ²									X			X		X		X		X	
Blood: Rituximab PK ²						X ⁷	X ⁷	X			X		X						

Study Day	Screening (up to 35 days prior to Day 0)	Day 0																General follow up period ¹	Individualized follow up period (IFU) ⁶	IFU Final Visit
		7 ± 1 days	28 ± 7 days	56 ± 7 days	70 ± 7 days	84 ± 7 days	112 ± 7 days	140 ± 7 days	168 ± 7 days	196 ± 7 days	224 ± 7 days	252 ± 7 days	280 ± 7 days	308 ± 7 days	336 ± 7 days	364 ± 7 days				
Study Week	W -5	W1	W4	W8	W10	W12	W16	W20	W24	W28	W32	W36	W40	W44	W48	W52	W68			
AE/SAE review	X ¹⁷	X	X	X	X	X	X	X	X	X	X	X	X	X	X	X	X ¹⁸	X		
Vital signs	X	X ^{3,4}	X ⁴	X	X ⁴	X ⁴	X	X	X	X	X	X	X	X	X	X	X	X	X	
12-lead ECG	X																			
CSSRS (suicidality assessment)		X ³	X	X	X	X	X	X	X	X	X	X	X	X	X	X	X			
Neurological assessment		X ³	X	X	X	X	X	X	X	X	X	X	X	X	X	X	X	X	X	
Urinalysis	X	X ³					X			X		X				X	X		X	
Blood: Immunoglobulin levels (IgG, IgA ² , IgM ²)	X	X ³		X	X	X	X	X	X	X	X	X	X	X	X	X	X	X	X	
Blood: Cryoglobulins	X					X			X			X				X	X		X	
Blood chemistry	X	X ³		X	X	X	X	X	X	X	X	X	X	X	X	X	X	X	X	
Hematology	X	X ³		X	X	X	X	X	X	X	X	X	X	X	X	X	X	X	X	
HIV, Hep B and Hep C screen	X ¹⁴																X			
Pharmacogenetics blood sample ¹⁵		X																		
Blood: Belimumab Immunogenicity ²		X ³			X				X							X	X			
Blood: Rituximab Immunogenicity ²					X ³				X							X				

Footnotes:

1. All subjects, including subjects who are withdrawn from the study (See Section 5.4.1) and decline to complete the treatment phase visits through Week 52, are required to enter the general follow up period. During this 16-week general follow up period, subjects will receive calls every 4 weeks (± 7 days) to evaluate AEs, to check concomitant medications and to complete the neurological assessment (Appendix 5).
2. In order to maintain the blind, sites will be blinded to these data following screening - including B-cell flow cytometry panels and IgA, IgM levels.
3. To be measured or collected pre-dose.
4. Subjects will be monitored post study treatment as detailed in protocol.

5. Biopsy can occur on Day 0 or at any time during the screening period provided the subject has met all other entry criteria prior to the biopsy.
6. Subjects will enter the IFU if, following the general follow up period, their CD19+ B-cell levels remain below the lower limit of normal (or less than 90% of baseline, if baseline value was below LLN). During the IFU, subjects will be seen in the clinic every 12 weeks (\pm 7 days), with calls every 4 weeks (\pm 7 days) between visits to evaluate subjects for AEs & concomitant medications. Subjects will exit the IFU when: CD19+ B-lymphocyte counts are within normal range or 10% of baseline levels (if baseline < LLN), OR at the investigator's discretion the subject starts receiving disease modifying therapy that may affect B-cell numbers OR or for up to a maximum of 2 years (i.e., up to Week 104) – whichever comes first. Subjects exiting IFU period will attend a final visit (within 28 days of that decision) for final assessments (IFU Final Visit) as detailed in the Table.
7. Obtain samples post-dose only, within 10 minutes after end of infusion.
8. Both doses of rituximab/placebo will be administered in the clinic. Approximately 60 minutes prior to rituximab/placebo, subjects will receive orally an antipyretic and an antihistamine. At least 30 minutes prior to administration of rituximab/placebo, subjects will receive IV 100mg methylprednisilone . The 2nd rituximab/placebo administration at the Week 10 visit must be given 14 days (13-18 days, see SRM) after the first administration (given at the Week 8 visit). A patient alert card should be sent home with the subject following each dose of rituximab/placebo.
9. If urine test is positive, confirm with serum test. Pregnancy testing & contraception are required until 16 weeks post last administration of study treatment for those subjects who complete Weeks 46- 52 or withdraw from treatment prior to Week 8 dosing. Pregnancy testing and contraception are required for approximately 12 months after the administration of the final rituximab/placebo dose for the subset of subjects who discontinue treatment from Week 8 up to Week 46.
10. Subjects will receive a reminder phone call 48 hours prior to efficacy assessment visits to remind them that they should not be using certain symptomatic therapies prior to visit (see Section 4.1 of Study Reference Manual for details); in addition subjects should document their last use of symptomatic therapies in their self injection log book.
11. First & second dose of belimumab will be administered in clinic by subject or caregiver. A patient alert card will be sent home with the subject each time belimumab is dispensed for home administration.
12. Week 24 biopsy may be taken on a separate day from the other required assessments within the Week 24 study visit window.
13. Week 52 biopsy is optional. Trancriptomics will only be performed if biopsy is taken.
14. If test otherwise performed within 3 months prior to first dose of study treatment, testing at screening is not required.
15. Informed consent for optional substudies e.g.,genetics must be obtained before collecting a sample.
16. If additional tests (e.g., pulmonary function tests, EMG, MRI) are required to complete ESSDAI assessment, these should be scheduled as close as possible to the stipulated study visit window.
17. From signing of consent until initiation of study treatment, only SAEs related to study participation will be collected.
18. From the end of general follow-up phase through the last contact (including the individualized safety follow-up phase), only designated AESIs (i.e., infections, malignancies, and depression/suicidality/self-injury), fatal SAEs, and SAEs assessed as related to the investigational product or to study participation will be collected.

